4.5.1.2. Main analytical approach

As there is only one post-baseline PET assessment within the first 6 months of the trial, mean change from baseline in amyloid plaque levels at Month 6 will be analyzed using an analysis of covariance model with the treatment group as fixed effect variable of interest, and APOE e4 genotype, baseline amyloid levels, and baseline age as the covariates. For the analysis of mean change from baseline at 12 and 18 months, a separate mixed model repeated measures (MMRM) analysis with data up to and including that specific time point will be used. This model will include the fixed effects of treatment, time, and treatment by time interaction, and APOE e4 genotype, and baseline amyloid level as covariates. Correlation among repeated measures on the same subject will be accounted for by enforcing an unstructured variance covariance matrix among the residuals. If the unstructured covariance structure matrix results in a lack of convergence, the following structures will be used in sequence until convergence is reached: heterogeneous Toeplitz covariance structure, heterogeneous autoregressive covariance structure,

heterogeneous compound symmetry covariance structure, and compound symmetry covariance structure. The Kenward-Roger approximation will be used to estimate the denominator degrees of freedom.

Time to amyloid plaque clearance between the two treatment groups will be analyzed and compared using a log-rank test for survival data. Kaplan-Meier estimates of percent of participants reaching amyloid plaque clearance and the p-value from the log-rank test will be used to determine the superiority of donanemab vs aducanumab in lowering time to plaque clearance.

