4.4. Co-Primary Endpoints Analysis

The primary objectives of this study are to test the hypothesis that participants treated with donanemab will have a significantly greater proportion of participants who reach amyloid plaque clearance compared to participants treated with aducanumab at the 6-month timepoint in both the ITT population and the intermediate tau subpopulation.

As the 6-month timepoint is the first scheduled opportunity to collect a post-baseline florbetapir F18 PET scan, the comparison of donanemab to aducanumab in complete brain amyloid clearance at 6 months will be performed using logistic regression. The logistic regression model will include fixed effect for treatment, ApoE $\epsilon 4$ genotype, baseline amyloid level, and baseline age. The test for this endpoint will be based on the contrast for the main effect of treatment from this logistic regression model. This analysis will be conducted on the full ITT population and the intermediate tau subpopulation. In case of quasi-complete separation of data points which may be possible due to small sample sizes, a Firth's penalized logistic regression model will be used to make inference on treatment efficacy.

Treatment effects from these logistic regression models will be summarized using estimated probabilities within each treatment group, along with odds ratios and a 100*(1- α)% confidence intervals, where α is the two-sided significance level for the primary endpoints.

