4.5.1.3. Sensitivity Analyses

Observed values for mean changes in centiloid values will be reported for 6-, 12-, and 18- month PET scans. Additionally, a last-observation-carried-forward (LOCF) mean change analysis in centiloid values will be reported.

Time to plaque clearance will also be analyzed using a Cox proportional-hazards model with the treatment group as fixed effect variable of interest, and APOE e4 genotype, baseline amyloid levels, and baseline age as covariates.

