4.5.1.4. Other secondary analyses

Mean percent change from baseline in brain amyloid plaque is defined as the specific time point PET centiloid value minus the baseline PET centiloid value, divided by the baseline PET centiloid value. These values will be modelled with the same approach as outlined for the mean change analyses.

Non-inferiority analyses will compare the changes in brain amyloid plaque levels for donanemab at 6 months to the changes in brain amyloid plaque levels for aducanumab at 12 months and at 18 months. The non-inferiority margin of interest is 5 centiloids. The MMRM models specified for the key secondary comparisons at 12 and 18 months will be used for the non-inferiority test, with appropriate contrasts and confidence intervals for the treatment-by-time interaction effects. For these non-inferiority analyses, if the upper bound of the 95% confidence interval for the donanemab vs. aducanumab contrasts is <5 centiloids, donanemab at 6 months will be considered to be non-inferior to aducanumab at that particular time point. An additional secondary objective to test the superiority of donanemab in amyloid plaque reduction at 6 months versus aducanumab at 12 months will also use this MMRM model and contrast.

For both the full study population and the intermediate tau subpopulation, the 12-month and 18-month comparison of proportion of participants with amyloid plaque clearance for donanemab versus aducanumab will include repeated post-baseline amyloid plaque clearance status (Yes/No) measurements and will be analyzed using separate generalized linear mixed model (PROC GLIMMIX) as pseudo-likelihood-based mixed effects repeated measures analysis assuming binomial distribution with a logit link. These models will be analyzed using data for outcomes up to and including the time point in question. The GLIMMIX model will include fixed effects for treatment, month, treatment-by-month interaction, APOE e4 genotype, baseline amyloid level, and baseline age as covariates. An unstructured variance-covariance matrix will be used to model the correlation among repeated measures on the same individual. If model convergence is not reached lesser restrictive variance-covariance structures will be employed until model convergence is attained.

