For the mean change from baseline in amyloid plaque levels for the intermediate tau subpopulation, the statistical models will be identical to that of the full population, with analysis of covariance applied to the 6-month data and an MMRM analysis applied to the 12- and 18-month data.

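### Baseline age is a covariate for the 6-month mean amyloid change but not for the 12- and 18-month MMRMs of the same variable, at a small cost in precision, and SAP 4.10 does not record where age was added to protocol models

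*SAP*

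**What the plan says.** SAP 4.5.1.2 specifies two models for change from baseline in centiloids. The 6-month ANCOVA has ApoE e4 genotype, "baseline amyloid levels, and baseline age as the covariates". The MMRM used for 12 and for 18 months has "fixed effects of treatment, time, and treatment by time interaction, and APOE e4 genotype, and baseline amyloid level as covariates", with no age term.

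The other covariate-adjusted amyloid models all carry age:

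- Co-primary logistic model (SAP 4.4): "genotype, baseline amyloid level, and baseline age".
- Cox model (SAP 4.5.1.3): "APOE e4 genotype, baseline amyloid levels, and baseline age as covariates".
- GLIMMIX for 12- and 18-month clearance (SAP 4.5.1.4): "treatment-by-month interaction, APOE e4 genotype, baseline amyloid level, and baseline age as covariates".

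SAP 4.5.1.4 and the text that follows it reuse the mean-change models:

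- Non-inferiority: "The MMRM models specified for the key secondary comparisons at 12 and 18 months will be used for the non-inferiority test". The superiority test of donanemab at 6 months against aducanumab at 12 months uses the same model.
- Percent change: "These values will be modelled with the same approach as outlined for the mean change analyses".
- Intermediate-tau mean change: "the statistical models will be identical to that of the full population".

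SAP 4.1 carries only the two stratification factors into models by default, so it does not bring age into the MMRM. SAP 4.1 and Protocol 9.3.1 both say that changes to the protocol's methods, with their justification, will be described in the SAP. SAP 4.10 reports none.

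For subgroups, SAP 4.8.3 reuses the co-primary and key secondary models and adds subgroup, subgroup-by-treatment and, where appropriate, subgroup-by-visit.

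**The concern.** The 6-, 12- and 18-month mean changes are three of the four key secondary endpoints tested in order under SAP 2.1. As written, only the first is age-adjusted. Donanemab's 6-month change would be age-adjusted in the ANCOVA and not age-adjusted in the MMRM that supplies the comparison with aducanumab at 12 and 18 months. An unexplained covariate difference between successive tests of one variable raises the question whether it was intended. That is hard to answer once PET values are unmasked.

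A second issue is the record. A reader who relies on SAP 4.10 would not learn that the co-primary model has a covariate that the supplied protocol does not list.

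**Working it through.** **Covariates side by side.** ApoE e4 genotype and baseline amyloid are in every model listed except the protocol's Cox model, for which no covariates are given. The table shows age only.

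| Model | Protocol | SAP |
|---|---|---|
| Co-primary logistic | 9.3.3: no | 4.4: yes |
| 6-month ANCOVA | 9.3.4.1: no | 4.5.1.2: yes |
| 12- and 18-month MMRM | 9.3.4.1: no | 4.5.1.2: no |
| GLIMMIX, 12- and 18-month clearance | 9.3.4.3: no | 4.5.1.4: yes |
| Cox | 9.3.4.2: optional, no covariates listed | 4.5.1.3: yes |

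The SAP therefore adds age to three models whose covariates the protocol specifies: logistic, ANCOVA and GLIMMIX. The MMRM is the exception within the SAP, but it is the model that still follows the protocol.

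**Reach of the MMRM.** Age is missing from the 12- and 18-month mean change, the 12- and 18-month percent change, the 12- and 18-month intermediate-tau mean change, and the contrasts of donanemab at 6 months with aducanumab at 12 or 18 months. The 6-month versions use the ANCOVA and have age. Clearance at 12 and 18 months, overall and in intermediate tau, uses the GLIMMIX and has age.

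**The plan's own figure.** The only related figure is the power of at least 98% for 6-month clearance (Protocol 9.5). With 35.7% against 3.0% and 2-sided alpha 0.05, power is 1.000 at 90 per arm and 0.985 at 45 per arm. The figure is reproduced and does not depend on this point.

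**Size of the precision loss.** Take n = 180 (Protocol 9.5, participants expected to have 6-month scans). Let r be the partial correlation of age with amyloid change given the other covariates. The documents give no value, so r is an assumption. Including age multiplies the residual variance by 1 − r², so the SE without age divided by the SE with age is 1/√(1 − r²). The equivalent loss of participants is 180r².

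| r | SE increase, formula | Participants lost, of 180 | SE ratio, simulated MMRM (12 and 18 months) | Power without age if 80% with it |
|---|---|---|---|---|
| 0 | 0% | 0 | 0.999 | 80.0% |
| 0.1 | 0.5% | 1.8 | 1.004 | 79.6% |
| 0.2 | 2.1% | 7.2 | 1.020 | 78.4% |
| 0.3 | 4.8% | 16.2 | 1.047 | 76.2% |

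The simulation fitted an unstructured-covariance MMRM with and without age (assumed SD 20 at each visit, residual correlation 0.7, 3,000 trials per setting). The cross-time contrasts gave the same ratios to within 0.1 percentage point. At r = 0.3 the 12-month SE was 3.134 centiloids without age and 2.993 with it, so the 95% CI half-width differs by 1.96 × (3.134 − 2.993) = 0.28 centiloids. With unequal SDs (16/20/24 or 24/20/16) the 18-month ratio at r = 0.3 was 1.041 or 1.046. The largest bias in any setting was 0.14 centiloids, with Monte Carlo error 0.10. In a separate ANCOVA simulation (90 per arm, 4,000 trials per setting), type I error was 0.047 to 0.052 with or without age.

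**Subgroup models (SAP 4.8.3).** The MMRM keeps treatment-by-time, so effects within each subgroup can still vary by visit. Without a three-way term, the between-subgroup difference in treatment effect is held constant over visits. It is then estimated as w′d, where d holds the true differences by visit, S is the residual covariance matrix and w = S⁻¹1/(1′S⁻¹1). Assume, for illustration only, d = 15, 7 and 0 centiloids at 6, 12 and 18 months:

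| SDs at 6/12/18 months | Correlation | 12-month model (true 7) | 18-month model (true 0) |
|---|---|---|---|
| 20/20/20 | any | 11.0 | 7.3 |
| 16/20/24 | 0.3 to 0.7 | 12.2 to 13.8 | 10.5 to 15.0 |
| 24/20/16 | 0.7 to 0.3 | 8.7 to 10.0 | −0.2 to 4.2 |

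With SDs 24/20/16 and correlation 0.7, the three weights are −0.114, 0.208 and 0.906. If the true difference is constant over visits, there is no error.

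**The case against.** The case for leaving the MMRM alone is substantial. It matches Protocol 9.3.4.1, contains both stratification factors as SAP 4.1 requires, and is valid with or without age. Nothing in the documents demands one covariate set across models. Any loss rests on an assumed correlation. Consistency could also be reached by removing age from the other models, which would make SAP 4.10 true against the supplied protocol.

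All of this stands, and it keeps the point small. It does not argue for leaving age out. If age is unrelated to amyloid change, including it costs about 0.1% of the SE; if it is related, precision is gained in two of the ordered key secondary tests.

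On the record, the SAP states age openly in its model descriptions, so nothing is concealed. What is missing is the justification and an accurate entry in 4.10. The SAP is based on the protocol dated 17 August 2021, which was not supplied. The Amendment (a) log and the visible part of the current summary of changes list no Section 9 change, so the models were probably the same then, but this cannot be confirmed.

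A reader might infer that every percent-change and intermediate-tau analysis lacks age. They do not: the 6-month ANCOVA versions and the GLIMMIX clearance analyses have it. A reader might also take the 12- or 18-month subgroup result as a plain average over visits. That does not follow either, because the weights depend on the covariance and can be negative.

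**Conclusion.** The inconsistency is real and of low severity. SAP 4.5.1.2 omits age from the 12- and 18-month mean-change models, while every other covariate-adjusted amyloid model has it. The cost is an SE about 0.5% to 4.8% larger for an assumed partial correlation of 0.1 to 0.3, and about nil at zero.

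A reader might conclude that the 12- and 18-month tests are biased, inflate type I error or depart from the protocol. The documents and the calculations support none of these. The co-primary conclusion and its power are not affected.

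SAP 4.10 is inaccurate against the supplied protocol, subject to the version caveat. The subgroup point is minor and outside the error-controlled tests. Its size depends entirely on assumed effects and SDs, and it affects neither the co-primary nor the 6-month ANCOVA subgroup analyses.

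**What to change.** Make these changes before the interim analysis or the 6-month database lock, because Protocol 6.3 keeps post-baseline PET values masked or scrambled until then.

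1. Add baseline age to the 12- and 18-month MMRMs in SAP 4.5.1.2. State that this carries over to the 12- and 18-month percent-change and intermediate-tau mean-change models, and to the contrasts of donanemab at 6 months with aducanumab at 12 and 18 months. The cost is one degree of freedom per model; age is already collected.
2. Record in SAP 4.10, with justification, that age was added to the logistic, ANCOVA and GLIMMIX models, and now to the MMRM, after checking against the 17 August 2021 protocol. This costs wording only.
3. In SAP 4.8.3, add subgroup-by-treatment-by-visit to the 12- and 18-month MMRM subgroup models and report the contrast at the named visit. Calling the two-way result a visit average would not be a sound substitute. The price is precision. With an even split (45 per cell), the 18-month by-visit SE is √(4 × 20²/45) = 6.0 centiloids, against 4.9 to 5.3 for the constant-difference model at correlation 0.5 to 0.7. Over the same correlations it is 7.2 against 4.5 to 4.7 with SDs 16/20/24, and 4.8 against 4.5 to 4.7 with SDs 24/20/16.

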9.3.4.1. Mean Change from Baseline in Amyloid Plaque

Consequently, mean change from baseline in amyloid plaque levels at Month 6 will be analyzed using an analysis of covariance method with the treatment group as fixed effect variable of interest, and APOE ϵ 4 genotype, and baseline amyloid levels as the covariates. For the analysis of mean change from baseline at 12 and 18 months, a separate mixed model repeated measures (MMRM) analysis with data up to that specific time point will be used. This model will include the fixed effects of treatment, time, and treatment by time interaction, and APOE ϵ 4 genotype, and baseline amyloid level as covariates. Correlation among repeated measures on the same subject will be accounted for by enforcing an unstructured variance covariance matrix among the residuals. If the unstructured covariance structure matrix results in a lack of convergence, the following structures will be used in sequence until convergence is reached: heterogeneous

Toeplitz covariance structure, heterogeneous autoregressive covariance structure, heterogeneous compound symmetry covariance structure, and compound symmetry covariance structure. The Kenward-Roger approximation will be used to estimate the denominator degrees of freedom.

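### The 12- and 18-month MMRM fits one baseline-amyloid slope for all visits; a baseline-by-time term would probably tighten those intervals slightly, at almost no cost

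*SAP*

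**What the plan says.** For mean change at 12 and 18 months, SAP 4.5.1.2 specifies separate MMRMs with "fixed effects of treatment, time, and treatment by time interaction, and APOE e4 genotype, and baseline amyloid level as covariates". Protocol 9.3.4.1 gives the same mean model. Neither lists a baseline-by-time term. The covariance is handled by "enforcing an unstructured variance covariance matrix among the residuals", with simpler structures as fallback. Each model is an "analysis with data up to and including that specific time point will be used", so the 12-month model has two post-baseline visits and the 18-month model has three.

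Month 6 is separate: "mean change from baseline in amyloid plaque levels at Month 6 will be analyzed using an analysis of covariance model". It therefore has its own baseline slope.

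SAP 4.5.1.4 extends the reach of the MMRM: "The MMRM models specified for the key secondary comparisons at 12 and 18 months will be used for the non-inferiority test". On the margin it says: "The non-inferiority margin of interest is 5 centiloids". The superiority contrast of donanemab at 6 months against aducanumab at 12 months, and the intermediate-tau mean-change analyses, reuse the same models.

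**The concern.** A main effect alone makes the regression of change on baseline identical at months 6, 12 and 18. There is reason to doubt that. Change is follow-up minus baseline centiloids (SAP 4.5.1.1), and clearance means a value below 24.1 (SAP 4.4.1). A cleared participant's change is therefore close to minus the baseline value, which is a slope near -1 among the cleared. The sample-size sections assume that the cleared share grows, so the pooled slope should steepen.

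If it does, one common slope fits some visits badly and the misfit goes into the residual variance. At stake is precision for two key secondary endpoints (mean change at 12 and 18 months) and for cross-visit contrasts that can carry misfit from both visits. Under the assumptions used below, the non-inferiority half-width is about 6 centiloids against a margin of 5, so avoidable width is unwelcome there.

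**Working it through.** **The plan's own figure.** The only stated operating characteristic is at least 98% power for 6-month clearance. With 35.7% v 3.0% and 45 per arm (half of about 90 evaluable, for intermediate tau), the pooled proportion is 0.1935 and

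z = [0.327 - 1.96 x sqrt(2 x 0.1935 x 0.8065/45)] / sqrt[(0.357 x 0.643 + 0.03 x 0.97)/45] = (0.327 - 0.163)/0.0758 = 2.16,

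which gives 98.5%. With 90 per arm, power exceeds 99.9%. The figure reproduces, but it does not involve the MMRM. No power or interval width is stated for the centiloid analyses.

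**Does the slope change?** Averaging the assumed clearance rates over the two arms gives
- month 6: (35.7 + 3.0)/2 = 19.4%
- month 12: (50.1 + 22.8)/2 = 36.5%
- month 18: (54.6 + 27.8)/2 = 41.2%

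The share rises, mostly before month 12. Centiloids were simulated to match the six rates and the 24.1 threshold, with assumed baseline mean 90-100 and SD 30-33. Under proportional removal the pooled slope went from about -0.33 to -0.52 at month 6 to about -0.60 to -0.70 at month 18. Under subtractive removal with a floor at zero it went from about -0.04 to -0.07 to about -0.13 to -0.18. It steepened in every scenario.

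**What a common slope costs.** Let beta_t be the visit slopes, S the residual covariance and SD_B the baseline SD. In large samples the fitted common slope is b = 1'S^-1 beta / 1'S^-1 1. The variance at visit t rises from S_tt to S_tt + SD_B^2 (beta_t - b)^2.

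Worked case, all inputs assumed: SD_B 30, residual SD 18/20/22, correlation 0.8. The weights on the three slopes are then 0.794, 0.278 and -0.072.
- Slopes -0.40/-0.55/-0.65: b = -0.424. The 18-month variance ratio is 1 + 900 x 0.2264^2/484 = 1.095, so the SE rises 4.7%.
- Slopes -0.30/-0.55/-0.70: b = -0.341. The ratio is 1 + 900 x 0.3594^2/484 = 1.240, so the SE rises 11.4%.
- Month 6 v 18 across arms, first set of slopes: 1 + 900 x (0.0236^2 + 0.2264^2)/(324 + 484) = 1.058, so the SE rises 2.8%.

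**Simulation.** 90 per arm, dropout missing at random, 500 replicates, SD_B 30, correlation 0.8, residual SD either 20 throughout or 18/20/22. Entries are the SE inflation of the planned model relative to one with baseline-by-visit slopes. NI is the non-inferiority contrast.

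| Slopes at 6/12/18 | 12 months | 18 months | NI v 12 | NI v 18 |
|---|---|---|---|---|
| equal | 0% | 0% | 0% | 0% |
| -0.40/-0.45/-0.50 | 0.0-0.1% | 0.3-0.7% | 0.1% | 0.3-0.5% |
| -0.40/-0.55/-0.65 | 0.7-1.5% | 2.1-4.9% | 0.7-1.0% | 2.0-3.1% |
| -0.30/-0.55/-0.70 | 2.4-4.5% | 5.8-12.1% | 2.0-2.8% | 5.0-7.8% |

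An extreme corner of the large-sample grid (correlation 0.9, residual SD 15/20/24, SD_B 35, steepest slopes) reached 39% at 18 months.

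**Calibrated to the plan's clearance rates.** The inflation was about 0-0.8% at 12 and 18 months and 0.1-1.6% for the non-inferiority contrasts. A second set of runs matched to the same rates agreed on 12 and 18 months (under 1%). Under proportional removal it gave about 1-5% for month 6 v 18 and 1-3% for month 6 v 12. Under subtractive removal it gave about 0.5% or less. The plan does not fix the other inputs that such runs need.

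**In centiloids.** For month 6 v 18 with residual SD 18/20/22, the half-width falls from 1.96 x 3.148 = 6.17 to 1.96 x 3.052 = 5.98 in the moderate case. In the steep case it falls from 1.96 x 3.275 = 6.42 to 1.96 x 3.038 = 5.95.

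**Validity.** Coverage stayed at 93-97% with either model when dropout did not depend on baseline differently by arm. When it did, in opposite directions by arm and with moderate slopes, the common slope gave a bias of 1.26 centiloids at 18 months (coverage 91.4%). With the added term the bias was -0.07 (coverage 95.2%).

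**The case against.** The strongest reply is that the planned model is legitimate and that no conclusion would turn on this. The documents state no centiloid slope and no rule that loss is proportional to baseline. They give only clearance rates, which flatten after month 12. If the slopes are equal, nothing is lost.

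Even under inputs that favour the extra term, decisions hardly move. Take baseline mean 100, SD 33 and removal of 55/72/78% v 18/45/58%. The 18-month difference is 78 - 58 = 20 centiloids with SE 2.83 or 2.73, so z is 7.1 or 7.3. Those inputs imply donanemab clearance of only about 11-25% at month 6, against the plan's 35.7%, so they probably exaggerate slope growth. In a companion scenario the month 6 v 18 SE falls from 2.87 to 2.77. At a true difference of zero, non-inferiority power then moves from Phi(5/2.87 - 1.96) = 41.4% to Phi(5/2.77 - 1.96) = 43.8%. The non-inferiority tests are other secondary objectives, outside the fixed testing sequence of SAP 2.1.

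Proportional loss would also make slopes differ by arm, which a pooled baseline-by-time term does not capture. It would leave percent change with no baseline slope at all.

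All of this stands as a limit on size and scope. None of it shows that the term is wrong or costly: with equal slopes, the mean SE was unchanged to one decimal place.

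**Conclusion.** The point holds as a conditional, small gain in efficiency. If the baseline slope changes between visits, which the plan's own definitions and clearance assumptions make likely, the 12- and 18-month mean-change intervals and the month-6-versus-12/18 intervals will be slightly wider than needed. The SE excess is about 0-1.6% in the main calibrated runs, with up to about 5% for month 6 v 18 in the second set. It is about 2-5% at 18 months under moderate assumed slope growth and up to about 12% under steep growth. Every figure depends on assumed SDs, correlations and slopes.

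A reader might infer more, and the documents do not support it:
- A common slope is not shown to be impossible. That needs a proportional-loss rule which appears nowhere.
- The key secondary family as a whole is not affected. Month 6 is an ANCOVA with its own slope, and time to clearance is a log-rank test.
- Type I error is not threatened under balanced dropout. The bias appeared only in a hypothetical dropout pattern that the documents do not predict, although the added term protects against it.

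**What to change.** In SAP 4.5.1.2, add baseline amyloid-by-time to the 12- and 18-month mean-change MMRMs, and state that least-squares means are evaluated at the overall mean baseline. Carry this to the analyses in SAP 4.5.1.4 that reuse these models: both non-inferiority contrasts, the 6-versus-12-month superiority contrast, and the 12- and 18-month intermediate-tau mean changes.

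The percent-change model need not change. Because SAP 4.5.1.4 has it follow the mean-change approach, say explicitly that the new term does not apply there. Protocol 9.3.4.1 lists the same covariates, so record the difference in SAP 4.10.

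The cost is a few lines of SAP text, one extra parameter in the 12-month model and two in the 18-month model, with about 180 participants expected to have 6-month scans.
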